**CONFIDENTIAL**

208710 (EPI-HPV-077 VS KR PMS)  
Protocol Amendment 1 Final

Note: The subject/subject's parent's/LAR's signature in the Informed Consent Form (ICF)/Informed Assent Form (IAF) signifies enrolment of the subject into the PMS. The ICF/IAF is for the collection and handling of safety information and **not** for the vaccination procedure.

- Safety monitoring:
  - Recording of all AEs during the 30 day period (**Day 1 to Day 30**) using diary cards after each dose of *Cervarix* is administered.
  - Recording of SAEs, adverse drug reactions (ADRs) and Pregnancy from the date of Visit 1 until 30 days (**Day 1 to Day 30**) after the last dose of *Cervarix* administered during the subject's participation in the PMS.
- Blood Samples: No blood samples will be collected in this PMS.
- Primary completion Date: last visit of Epoch 1.  
Refer to [GLOSSARY OF TERMS](#) for the definition of PCD.
- End of Study (EoS): Last subject last visit (Follow up after the last dose)  
Refer to [GLOSSARY OF TERMS](#) for the definition of EoS.
- Duration of the PMS: The intended duration of this study is approximately 4 years.
  - Epoch 001: Prospective data collection starting at vaccination dose 1 and ending at follow up after *last dose*.

The below table presents the study group and the epoch foreseen in the PMS study.

- **Study groups:** The study groups and epoch foreseen in the study are provided in [Table 1](#).

**Table 1      Study group and epoch foreseen in the study**

Study groups	Number of subjects	Age at Dose 1 (Min/Max)	Epoch 001
HPV Group	Approx. 600	9/25 years	X

- Type of PMS: Self-contained.
- Data collection: Standardised hard copy Case Report Form (CRF). SAEs, ADRs and pregnancy information will be collected by using the SAE, ADR and Pregnancy Reporting Form.

### **3.1.      Discussion of PMS design (Amended: 14 May 2018)**

All adverse events reported during the 30-day post-vaccination follow-up period and all SAEs reported throughout the PMS period up to 30 days (**Day 1 to Day 30**) after the last dose of *Cervarix* administered during the subject's participation in the PMS, will be collected as part of safety data in this PMS. These adverse events will be further classified by GSK at the time of statistical analyses as expected/unexpected based on the locally approved Prescribing Information.

**CONFIDENTIAL**208710 (EPI-HPV-077 VS KR PMS)  
Protocol Amendment 1 Final

## 4. STUDY POPULATION

### 4.1. Number of subjects/centres (Amended: 14 May 2018)

As per the MFDS (Korea) requirements, safety information from a total of at least 600 evaluable subjects is needed for this PMS. Therefore, a total of at least 600 evaluable subjects will be enrolled over a period of 4 consecutive years.

#### 4.1.1. Recruitment of PMS centres

Overview of the recruitment plan:

- This prospective, observational PMS will be conducted at multiple centres **in** private clinics and hospitals (**department of pediatrics and obstetrics & gynecology, etc.**) in Korea for a period of 4 years.
- PMS population: Subjects who receive at least one dose of *Cervarix* as a part of routine practice at a clinic or hospital. Only subjects to whom *Cervarix* will be prescribed in routine clinical practice will be invited to participate in the surveillance.
- Eligible subjects may join the PMS after the ICF/IAF has been signed by the subject/subject's parent/LAR.
- The PMS is required to be conducted in at least one hospital [with Institutional Review Board (IRB) oversight] in order for the PMS to be conducted in private clinics (without IRB).
- Target enrolment: A total of at least 600 subjects will be enrolled over a period of 4 years
- The vaccine will be purchased by the subject/subject's parents/LAR.
- The recruitment will be monitored by the PMS monitor.

**Table 2      Expected enrolment plan of subject**

Period	Tentative calendar dates	Planned No. of enrolled subject*
1 st Year	2017.07.28 ~ 2018.07.27	0
2 nd Year	2018.07.28 ~ 2019.07.27	280
3 rd Year	2019.07.28 ~ 2020.07.27	300
4 th Year	2020.07.28 ~ 2021.07.27	20
Total		600**

\* Approximate number

\*\* At least 600 evaluable subjects will be recruited for the PMS.

Note: The above plan may be modified depending on conditions such as progress

**CONFIDENTIAL**208710 (EPI-HPV-077 VS KR PMS)  
Protocol Amendment 1 Final**4.2. Inclusion criteria for enrolment**

Deviations from inclusion criteria are not allowed because they can potentially jeopardise the scientific integrity and regulatory acceptability of the study or subject safety. Therefore, adherence to the criteria as specified in the protocol is essential.

All subjects must satisfy ALL the following criteria at PMS entry:

- Subject or/and subjects whose parent(s)/Legally Acceptable Representative(s) [LAR(s)], in the opinion of the investigator, can and will comply with the requirements of the protocol (e.g., complete the diary cards, return for follow-up visits).
- Korean male or female subjects aged 9-25 years who are eligible for the series of *Cervarix* according to the locally approved PI.
- Written informed consent obtained from the subject/from the parent(s)/LAR of the subject.

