**3. PMS DESIGN OVERVIEW (AMENDED: 14 MAY 2018)**

Sequential Allocation of Subject Numbers					
Cervarix (N ~ 600)					
Vaccination Dose 1	Follow-up 30-day follow-up after Dose 1	Vaccination Dose 2	Follow-up 30-day follow-up after Dose 2	Vaccination Dose 3	Follow-up 30-day follow-up after Dose 3

N: Number of subjects planned to be enrolled

PMS conclusion will depend on the concluding visit of the subject in the PMS.

Definition of Conclusion of PMS for a subject: Subjects who have completed 30-day follow-up after at least one dose, regardless of the number of doses, are considered to have completed the PMS.

Note: Eligible subjects can be enrolled at any stage in the PMS regardless of Cervarix dose(s) received previously.

Follow-up for AEs will continue for 30 days after receiving each vaccine dose(s) in the PMS. Follow-up of SAEs will continue from the date of Visit 1 until 30 days after the last dose received in the PMS. Cervarix will be vaccinated according to local practice

Protocol waivers or exemptions are not allowed unless necessary for the management of immediate safety concerns. Therefore, adherence to the study design requirements, including those specified in the outline of study procedures (Section 8), are essential and required for study conduct. ***This PMS will be conducted by a continuous surveillance method.***

- PMS design: A prospective, observational, non-comparative, multi-centre PMS in Korea.
- Study population: 9-25 years old males and females.
- Vaccination schedule: Cervarix will be administered as per the local PI in Korea.

The recommended schedule is as follows:

- Vaccination: The 9-25 years old subjects should be administered Cervarix with 3 doses (**0.5mL each**), 0, 1, and 6 months schedule. The 9-14 years old subjects can be vaccinated with 2 doses, 0 and 6-12 months schedule. ***In the 2-dose schedule, if the second dose is administered before 5 months after the first dose, the third dose vaccination is required. In the 3 doses schedule, if the vaccination schedule requires flexibility, the second dose can be administered between 1 and 2.5 months and the third dose can be administered between 5 and 12 months after the first dose.***

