### **10.2. Subject withdrawal (Amended: 14 May 2018)**

Subjects who are withdrawn because of SAEs/AEs must be clearly distinguished from subjects who are withdrawn for other reasons. Physicians will follow subjects who are withdrawn as result of a SAE/AE until resolution of the event (see Section 8.5).

Withdrawals will not be replaced.

**CONFIDENTIAL**208710 (EPI-HPV-077 VS KR PMS)  
Protocol Amendment 1 Final**10.2.1. Subject withdrawal from PMS**

From an analysis perspective, a ‘withdrawal’ from the PMS refers to any subject who did not come back for the concluding visit/was not available for the concluding contact foreseen in the protocol.

All data collected until the date of withdrawal/last contact of the subject will be used for the analysis.

A subject is considered a ‘withdrawal’ from the PMS when no PMS procedure has occurred, no follow-up has been performed and no further information has been collected for this subject from the date of withdrawal/last contact.

Physicians will make **attempts** to contact those subjects who do not return for scheduled visits or follow-up.

Information relative to the withdrawal will be documented in the CRF. The physician will document whether the decision to withdraw a subject from the PMS was made by the subject’s parent(s) or LAR(s), or by the physician, as well as which of the following possible reasons was responsible for withdrawal:

- Serious adverse event.
- Non-serious adverse event.
- Protocol violation (specify).
- Consent withdrawal, not due to an adverse event.
- Lost to follow-up.
- Death.
- Other (specify).

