## 11.2. Determination of sample size

According to MFDS (Korea) regulation requirement, at least 600 evaluable subjects will be recruited for the PMS. Therefore, 660 subjects are expected to be enrolled through the PMS period considering the dropout rate of 10% (out of 600 subjects). Depending on the status, the enrolment plan can be adjusted.

**Table 6** presents the exact two-sided 95% confidence interval for a sample size of 600 subjects.

**Table 6      Exact two-sided 95% CI for the percentage of subjects reporting at least one symptom with a sample size of 600 subjects**

Observed rate expressed as a percentage (number of subjects reporting at least one symptom*)	Exact two-sided 95% CI for this observed rate for a sample size of 600 subjects	
	Lower limit (LL)	Upper limit (UL)
1%	0.4	2.2
2%	1.0	3.5
3%	1.8	4.7
4%	2.6	5.9
5%	3.4	7.1
10%	7.7	12.7
15%	12.2	18.1
20%	16.9	23.4

\*: The symptom could be any one of expected AE, unexpected AE or SAE.

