2.2 Number of Subjects

According to Ministry of Food and Drug Safety (MFDS) (Korea) regulation requirement, at least 600 evaluable subjects will be recruited for the post-marketing surveillance (PMS). Therefore, 660 subjects are expected to be enrolled through the PMS period considering a dropout rate of 10% (out of 600 subjects). Depending on the status of enrollment, the plan can be adjusted.

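### Table 2 and the Section 3 diagram plan 600 enrolled subjects, omitting the 60-subject dropout allowance behind the 660 in Protocol 11.2 and SAP 2.2

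*Protocol*

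**What the plan says.** Protocol 11.2 sets the requirement at no fewer than 600 evaluable subjects and derives the enrolment from it: "660 subjects are expected to be enrolled through the PMS period considering the dropout rate of 10% (out of 600 subjects"). SAP 2.2 repeats this almost word for word: "660 subjects are expected to be enrolled through the PMS period considering a dropout rate of 10% (out of 600 subjects"). Both add that the enrolment plan can be adjusted.

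Other current parts of the protocol give 600:

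- **Table 2** (year-by-year enrolment plan). Under the header "Planned No. of enrolled subject" the four years are 0, 280, 300 and 20, with a total of 600. The footnote on that total reads "At least 600 evaluable subjects will be recruited for the PMS". The column is marked approximate, and a note allows the plan to be modified.
- **Section 3 diagram.** It shows N of about 600, with the key "N: Number of subjects planned to be enrolled".
- **Section 4.1.** "a total of at least 600 evaluable subjects will be enrolled over a period of 4 consecutive years".
- **Section 4.1.1.** "Target enrolment: A total of at least 600 subjects will be enrolled over a period of 4 years".
- **Table 1 and Synopsis table 1.** Both give the number of subjects as approximately 600, without saying whether that means enrolled or evaluable.

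Section 10.2 adds: "Withdrawals will not be replaced".

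**The concern.** Enrolled and evaluable are different counts in this protocol. A subject is enrolled when the consent or assent form is signed. The glossary's definition of evaluable also requires eligibility and compliance with protocol procedures, and SAP 4.1 lists seven grounds for leaving a subject out of the safety analysis set. The dropout allowance in 11.2 exists to bridge the two counts.

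Table 2 and the Section 3 diagram attach the evaluable number to the word enrolled, so the bridge is missing from the yearly schedule. Table 2 also describes one number in two ways: enrolled in its header, evaluable in its footnote.

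What is at stake is the regulator's minimum. Anyone tracking recruitment against Table 2 would see the plan as complete at 600 enrolled, with no margin for loss. Because the last year is planned at only 20 subjects, the missing 60 is three times that year's intake, so a shortfall noticed late would be hard to make up at the planned pace.

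**Working it through.** **Inputs.** Evaluable minimum 600 (Protocol 4.1 and 11.2); dropout 10%, taken on 600 (Protocol 11.2, SAP 2.2); yearly enrolment 0, 280, 300, 20 (Table 2); no replacement of withdrawals (Protocol 10.2); exact two-sided 95% intervals (Protocol 11.2 and Table 6).

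**The plan's own enrolment figure.** Allowance = 0.10 × 600 = 60. Enrolment = 600 + 60 = 660. This reproduces 11.2 and SAP 2.2 on their stated base.

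**Table 2.** 0 + 280 + 300 + 20 = 600. The addition is correct.

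**Gap.** 660 − 600 = 60 subjects, which is 60/660 = 9.1% of the expected enrolment and 100% of the allowance.

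**Consequence for the evaluable count, with 60 unreplaced losses.**

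| Enrolled | Evaluable after 60 losses | Losses possible before falling below 600 |
|---|---|---|
| 600 (Table 2, Section 3) | 600 − 60 = 540 | 600 − 600 = 0 |
| 660 (11.2, SAP 2.2) | 660 − 60 = 600 | 660 − 600 = 60 |

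**Consequence for precision.** All eight rows of Table 6 reproduce with Clopper-Pearson limits at n = 600. Comparing 600 with 540 evaluable:

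| Result | n = 600 | n = 540 |
|---|---|---|
| 10% observed (60/600; 54/540), exact 95% CI | 7.72% to 12.68% | 7.60% to 12.85% |
| No events, exact two-sided 95% upper limit, 1 − 0.025^(1/n) | 0.61% | 0.68% |

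**Base of the 10%.** The 660 rests on 10% of 600. If 10% of those enrolled were lost instead, 660 × 0.90 = 594 would remain, and 600/0.90 = 666.7, rounded up to 667, would be needed. That is a separate question and does not affect the 600-versus-660 conflict.

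**The case against.** The best defence is that nothing caps enrolment at 600. Table 2 read with its footnotes is approximate, modifiable and tied to a floor of 600 evaluable, so a sponsor following all of it would go on recruiting until that floor was met. Section 4.1 states the same floor. Section 4.1 also uses enrolled loosely for the evaluable target, so the Table 2 footnote may be imprecise wording and not a rival target. The allowance appears in the sample size section, where it belongs, and the SAP agrees. Continued recruitment to a floor is not replacement of withdrawals. A subject counts as complete after 30-day follow-up of a single dose, so later losses need not reduce the count. No analysis depends on the difference.

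Much of this stands, and it keeps the point minor. The 540 is the plan's own assumed loss applied to an enrolment held at 600, not a prediction. Sections 4.1 and 4.1.1, Table 1 and Synopsis table 1 can all be read consistently with 660.

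The defence does not reconcile Table 2 and Section 3 with 11.2. A gap equal to the entire allowance is not rounding, and a right to revise a plan does not make it consistent now. If the footnote governs, the Table 2 header is wrong; the Section 3 diagram has no such footnote and says plainly that N is planned enrolment.

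**Conclusion.** The concern holds. The protocol gives two figures for planned enrolment, 600 in Table 2 and the Section 3 diagram and 660 in 11.2 (repeated in SAP 2.2). They differ by 60 subjects, exactly the dropout allowance. The individual sums are correct; the error is that the allowance was not carried into the enrolment plan.

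The effect is operational and regulatory: if enrolment followed the yearly figures and stopped at 600, any loss would miss the minimum. Inference is essentially untouched, since this is a descriptive surveillance and even 540 evaluable subjects would widen the intervals only slightly. The conclusion takes 660 as the documents' own figure, on their stated base of 10% of 600. It is worth correcting, at low priority.

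**What to change.** - Change the Table 2 total and the Section 3 N to about 660 enrolled. The sponsor should choose how the additional 60 are spread over the years.
- Label 600 as evaluable wherever it appears, so that the Table 2 header and footnote no longer describe one number in two ways.
- For consistency, add the word evaluable to the target in 4.1.1, and state in Table 1 and Synopsis table 1 whether about 600 means enrolled or evaluable.
- Leave 11.2 and SAP 2.2 as they are for this point.

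The cost is table and wording edits in the protocol. No subjects are added beyond the 660 that 11.2 already expects, and the SAP does not change.

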**4.3. Exclusion criteria for enrolment**

Deviations from exclusion criteria are not allowed because they can potentially jeopardise the scientific integrity and regulatory acceptability of the study or subject safety. Therefore, adherence to the criteria as specified in the protocol is essential.

The following criteria should be checked at the time of PMS entry. If **ANY** exclusion criterion applies, the subject must not be included in the PMS:

- At the time of PMS entry, the contraindications and precautions of use indicated in the locally approved PI. PI should be checked and the subject must not be included in the PMS if there is any contraindication. Any changes in the locally approved PI must be implemented immediately.
- Subjects who had previous administration of a HPV vaccine other than *Cervarix* will not be enrolled into the study
- Subjects who are not eligible for vaccination with *Cervarix* according to the medical judgement of physician.
- Child in care. Please refer to the [GLOSSARY OF TERMS](#) for the definition of child in care.

**5. CONDUCT OF THE PMS****5.1. Regulatory and ethical considerations, including the informed consent process**

The PMS will be conducted in accordance with the ICH Guideline for GCP or other applicable guidelines (local rules and regulations of the country (MFDS) (Korea) and relevant GSK SOPs/Policies and Guidance), all applicable subject privacy requirements and the guiding principles of the Declaration of Helsinki.

**CONFIDENTIAL**

208710 (EPI-HPV-077 VS KR PMS)  
Protocol Amendment 1 Final

The study has been designed and will be conducted in accordance with the ICH Harmonised Tripartite Guideline for clinical investigation of medicinal products in the paediatric population (ICH E11) and all other applicable ethical guidelines.

GSK will obtain favourable opinion/approval to conduct the PMS from the appropriate regulatory agency, in accordance with applicable regulatory requirements, prior to a site initiating the PMS in that country.

Conduct of the PMS includes, but is not limited to, the following:

- Institutional Review Board (IRB)/Independent Ethics Committee (IEC) review and favourable opinion/approval of PMS protocol and any subsequent amendments.
- Subject/ subject's parent(s)/LAR(s) informed consent and subject informed assent, as appropriate
- Physician reporting requirements as stated in the protocol.

GSK will provide full details of the above procedures to the physician, either verbally, in writing, or both.

Freely given and written or witnessed/ thumb printed informed consent must be obtained from each subject or subject's parent(s)/LAR(s) and subject informed assent prior to participation in the PMS.

GSK Biologicals will prepare a model ICF which will embody the ICH GCP or other applicable guidelines and GSK Biologicals required elements. While it is strongly recommended that this model ICF is to be followed as closely as possible, the informed consent requirements given in this document are not intended to pre-empt any local regulations which require additional information to be disclosed for informed consent to be legally effective. Clinical judgement, local regulations and requirements should guide the final structure and content of the local version of the ICF.

In accordance with the ICH Harmonised Tripartite Guidelines for Good Clinical Practice, a subject who can only be enrolled in the study with the consent of her parent(s) or legally acceptable representative (e.g., minors), should be informed about the study to the extent compatible with the subject's understanding and, if capable, the subject should sign and personally date a written IAF. It is required that the assent be signed by each subject, if capable, in addition to the informed consent that is to be signed by her parent or legal representative. It should be assessed whether an assent is required depending on the age of the study population and the local requirements.

The physician has the final responsibility for the final presentation of the ICF and IAF, respecting the mandatory requirements of local regulations. The ICF and IAF generated by the physician with the assistance of the sponsor's representative must be acceptable to GSK Biologicals and be approved (along with the protocol, and any other necessary documentation) by the IRB/IEC.

**CONFIDENTIAL**208710 (EPI-HPV-077 VS KR PMS)  
Protocol Amendment 1 Final

## 6. DETAILED PMS PROCEDURES

### 6.1. Subject identification

Subject numbers will be assigned sequentially to subjects who participate/whose parents/LARs consent to allow their children to participate in the PMS, according to the range of subject numbers allocated to each PMS centre.

### 6.2. General PMS aspects

Supplementary PMS conduct information not mandated to be present in this protocol is provided in the accompanying Study Procedure Manual (SPM). The SPM provides the physician and the site personnel with administrative and detailed technical information that does not impact the safety of the subjects.

### 6.3. Outline of PMS procedures (Amended: 14 May 2018)

*Table 3* presents the list of PMS procedures.

**CONFIDENTIAL**208710 (EPI-HPV-077 VS KR PMS)  
Protocol Amendment 1 Final**Table 3 List of PMS procedures**

Epoch	Epoch 001		
Type of contact	Visit 1	Visit 2	Visit 3 c
Informed consent *	●		
Check inclusion/exclusion criteria *	●		
Check contraindications	●	●	●
Check warnings and precautions	●	●	●
Collect demographic data	●		
Medical history *	●		
Medication/Vaccination history **	●		
Physical examination	●	0	0
Pre-vaccination body temperature	●	●	●
Record vaccination information	●	●	●
Distribution of diary cards	0	0	0
Recording of adverse events within 30 days post-vaccination, by physician	●	●	●
Return of diary cards a		0	0
Diary card transcription by physician		●	●
Record any concomitant medication/vaccination	●	●	●
Record any intercurrent medical conditions		●	●
Reporting of serious adverse events / ADRs/Pregnancy Information	●	●	●
PMS Conclusion b	●	●	●

● is used to indicate a PMS procedure or a vaccination-related non-PMS procedure that requires documentation in the individual CRF.

○ is used to indicate a PMS procedure that does not require documentation in the individual CRF.

\* For the subjects who have received Cervarix previously and are enrolled in the PMS, procedures for Informed Consent/Check inclusion/exclusion criteria/Medical history/Vaccination history can be conducted at the first PMS-related visit.

\*\* **Medication/Vaccination history** (within 30-days prior to the Cervarix vaccination)

For subjects who have received one or two dose/s of Cervarix before the PMS enrolment, previous Cervarix vaccination history will be reported starting at the first PMS-related visit onwards irrespective of the number of dose subject received during the PMS.

a – The subjects will be instructed to return the completed diary card to the physician on their next PMS visit or phone or mail, to report any AEs/SAEs/ADRs/Pregnancy during the 30 day period (**Day 1 to Day 30**) using diary cards after each dose of Cervarix is administered.

b –PMS CRF Conclusion section to be completed depending on the available concluding visit of the subject in the PMS. The CRF conclusion will be 30 days after the last dose.

c –*The visit 3 can be omitted as 9-14 years old can be vaccinated with two dose schedule.*

It is the physician's responsibility to ensure that the dosing intervals are followed as described in the locally approved PI. However, if circumstances dictate other intervals, this will not lead to the exclusion of the subject from the analysis.

